**A Single-Center Clinical Study to Evaluate the
Efficacy and Safety of Sutureless Ophthalmic Hydrogel
for Corneal Wound Repair**

NCT Number: Not applicable

Document Date: January 2026

Version: V1.0

A Single-Center Clinical Study to Evaluate the Efficacy and Safety of Sutureless Ophthalmic Hydrogel for Corneal Wound Repair

Research Unit: Eye Hospital of Shandong First Medical University
(Shandong Eye Hospital)

Principal Investigators: [name], [name], [name]

Protocol Summary

Study Title: A Single-Center Clinical Study to Evaluate the Efficacy and Safety of Sutureless Ophthalmic Hydrogel for Corneal Wound Repair.

Study Objective: To evaluate the safety and efficacy (therapeutic effect) of a sutureless ophthalmic hydrogel for repairing corneal defects in patients with corneal lamellar defects.

Study Subjects: Patients with corneal stromal defects caused by various etiologies, including those resulting from trauma or surgical lesion excision, without corneal perforation.

Study Design: Investigator-initiated, single-center, single-arm, open-label, single-dose trial.

Planned Number of Subjects:

A total of 30 cases

Study Period and Expected Participant Involvement Duration:

Study Period: April 2026 – April 2027

Expected Participant Involvement Duration:

The expected participation period for each subject in this clinical study is from the date of consent to the end of the observation period.

Contact Information:

[contact]

Responsible Person: [name]

1. Background Information

The cornea is a transparent tissue on the ocular surface that is vulnerable to trauma and infection. Corneal transplantation remains the primary treatment for corneal blindness. Due to a shortage of donor corneas and high surgical costs, 12.7 million patients worldwide are waiting for corneal donors, and only 1 in 70 patients receives corneal transplantation annually [1]. After corneal transplantation, the risk of graft failure due to immune rejection is lifelong. Therefore, addressing the shortage of donor corneas and developing new corneal grafts with good histocompatibility and low immunogenicity is highly desirable. A paradigm shift in corneal stromal repair is needed, analogous to the use of liquid sealants for filling tooth defects in dentistry. In corneal surgery, injectable hydrogels that require no sutures, adhere tightly to the corneal bed after implantation, and achieve anatomical repair are urgently needed

in clinical practice. With advances in ophthalmic biomaterials, various injectable corneal hydrogels have been developed. These materials have demonstrated excellent wound repair and pro-regenerative capabilities in animal studies.

Current clinical interventions for corneal injuries primarily include corneal suturing [2], corneal transplantation [3], conjunctival flap coverage [4], multilayer amniotic membrane transplantation [5], soft contact lens application [6], and injectable sealants [7]. Injectable sealants offer a rapid, sutureless repair method. In many ophthalmology centers, injectable corneal sealants are used for emergency management of corneal perforation caused by trauma or persistent ulcers.

Injectable corneal sealants mainly include cyanoacrylate glue, fibrin glue, and polyethylene glycol (PEG) gel. Cyanoacrylate glue offers the advantages of easy application and rapid sealing, and has been used for emergency closure of corneal perforations for over 50 years [8]. However, incomplete polymerization of cyanoacrylate glue leaves residual toxic monomers, and its degradation products release formaldehyde, alkyl cyanoacrylates, and other toxic compounds [9]. These toxic substances can irritate the cornea, leading to scarring and neovascularization, often necessitating subsequent corneal transplantation. Fibrin glue and PEG gel exhibit good histocompatibility and biodegradability in corneal repair [10, 11]. Nevertheless, these adhesives have drawbacks such as a narrow application window, poor adhesion, and the need for multi-component mixing, which limit their clinical use [12, 13]. Currently, there remains a lack of an injectable material that is convenient, exhibits good histocompatibility, and promotes corneal regeneration.

A hydrogel is a three-dimensional polymeric network with water-retaining capacity [14]. Hydrogel materials possess favorable mechanical properties,

cytocompatibility, and optical characteristics, making them suitable for the regeneration and repair of damaged corneas [15]. With advances in ophthalmic biomaterials, various types of hydrogels have been applied for corneal stromal repair. Based on clinical application type, corneal hydrogels can be categorized into preformed hydrogels and injectable hydrogels [16]. Preformed hydrogels are represented by collagen-based hydrogels [17]. Clinical studies have found that suture fixation of collagen-based hydrogels tends to cause graft degradation and stromal scar formation, limiting their further clinical application [18].

Injectable hydrogels are stimuli-responsive materials. Their liquid precursors, after injection into tissue defects, rapidly crosslink into solid gels under external stimuli or coupling agents. This minimally invasive delivery reduces patient discomfort, infection risk, recovery time, and costs, making them promising for wound repair [19]. Recent studies show that injectable corneal hydrogels overcome limitations of preformed hydrogels, offer good histocompatibility, enable sutureless repair of various stromal defects and perforations, and promote regeneration of epithelium, stroma, and nerves, potentially serving as an alternative to corneal transplantation [20].

Significant progress has been made in preclinical studies of injectable corneal hydrogels, demonstrating efficacy in repairing corneal ulcers and replacing conventional corneal transplantation in animal models; however, no reports on their clinical efficacy and safety are available.

2. Objectives

2.1 Primary Objective

The primary objective of this clinical study is to evaluate the safety of a sutureless ophthalmic hydrogel for repairing corneal lamellar defects. Safety will be assessed based on diagnostic and clinical examination findings, including the occurrence, severity, and frequency of all adverse

events (including systemic symptoms).

2.2 Secondary Objective

The secondary objective of this clinical study is to evaluate the efficacy (therapeutic effect) of the sutureless ophthalmic hydrogel for repairing corneal lamellar defects, using corneal thickness and corneal clarity as the primary outcome measures.

3. Study Design

3.1 Study Type

Investigator-initiated exploratory clinical study

3.2 Study Design

Investigator-initiated, single-center, single-arm, open-label, single-dose trial.

3.3 Evaluation Items

3.3.1 Primary Evaluation Items: Safety Evaluation Items

① Safety Evaluation Items (Systemic)

To evaluate the type, severity, and frequency of all related adverse events.

② Safety Evaluation Items (Ophthalmic)

- Intraocular pressure (IOP)
- Ocular surface inflammatory reaction
- Infection
- Corneal endothelial morphology and density

- Corneal epithelial healing time
- Hydrogel displacement or detachment

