9.4 Adverse Events Recording

If a new adverse event occurs during the study period, record the following items in the adverse event column of the case report form.

Event name

Onset date

Severity

Outcome (recovery, improvement, unrecovered, death, unknown)

Outcome date

Correlation with trial procedures and transplantation of autologous

urine-derived epithelial cells

Management (discontinuation/continuance of the study, and treatment content for the adverse event)

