10.1 Safety Evaluation Items

The primary safety evaluation item: [All adverse events including systemic symptoms].

The secondary safety evaluation items: [Adverse events caused by hydrogel filling] and [Adverse events caused by surgical procedures], which mainly include elevated intraocular pressure, ocular surface inflammatory reaction, hydrogel displacement or detachment, corneal infection, delayed corneal epithelial healing, and decreased corneal endothelial morphology and density, with the judgment criteria

determined by the investigator.

Primary Outcome Measures and Judgment Criteria:

Delayed corneal epithelial healing

Judgment criteria: Corneal epithelium remains unhealed for 7 consecutive days as specified in 7.4.2. If delayed healing is observed during follow-up, timely adjustment of medication is required.

Infection

Judgment criteria:

- ① Severe conjunctival hyperemia accompanied by ciliary hyperemia and purulent discharge as per 7.4.1 (Conjunctival findings);
- ② Corneal infiltration and decreased corneal clarity in the hydrogel-filled area as per 7.4.2 (Corneal findings).

Infection is diagnosed when either ①+② or ② alone is present.

Hydrogel detachment

Judgment criteria:

- ① Depression in the hydrogel-filled area as observed under 7.4.2 (Corneal findings);
- ② Decreased thickness of the hydrogel-filled area detected by corneal OCT (7.3.3);
- ③ Decreased corneal thickness in the hydrogel-filled area detected by corneal topography (7.3.4).

Hydrogel detachment is diagnosed when ① and/or ② and/or ③ is present.

Furthermore, considering the occurrence of side effects and abnormal changes in clinical laboratory values during this clinical study, the overall safety of each subject will be graded into the following four categories:

- ① **Safe:** No side effects or abnormal changes in clinical laboratory values during the study period.
- ② **Basically safe:** Mild study-related side effects occurred during the study period (relieved/resolved without special treatment), or clinically insignificant abnormal changes in clinical laboratory values occurred (resolved upon re-examination without

intervention).

③ **Safety concerns:** Moderate study-related side effects occurred during the study period (relieved/resolved only after symptomatic treatment), or clinically significant abnormal changes in clinical laboratory values occurred (requiring intervention/re-examination monitoring).

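### The primary safety item is all related adverse events in 3.3.1 but all adverse events in 2.1 and 10.1, and the causality item in 9.4 names a product that is not in this trial

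*Protocol*

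**What the plan says.** Protocol 2.1 sets the primary objective as safety, judged on "the occurrence, severity, and frequency of all adverse" events, with systemic symptoms included. Protocol 10.1 agrees: "The primary safety evaluation item: [All adverse events including systemic symptoms". It then names as secondary "Adverse events caused by hydrogel filling] and [Adverse events caused by surgical procedures".

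Protocol 3.3.1, which lists the primary evaluation items, differs. Its systemic sub-item is "To evaluate the type, severity, and frequency of all related adverse events". A separate ophthalmic sub-item lists intraocular pressure, ocular surface inflammation, infection, endothelium, epithelial healing time, and hydrogel displacement or detachment. That list carries no relatedness limit.

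Protocol 10.1 puts the same six ophthalmic topics under the secondary safety items. It then gives criteria for delayed epithelial healing, infection and detachment under a heading that calls them primary outcome measures. Protocol 2.2 describes the secondary objective as "using corneal thickness and corneal clarity as the primary outcome measures".

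On causality, 9.2.6 sets a four-category judgement of the relation to the trial procedures and the hydrogel repair, taken together. The matching item to be recorded under 9.4 is "Correlation with trial procedures and transplantation of autologous" "urine-derived epithelial cells". Section 8.1 gives the product as decellularized porcine corneal stroma with methacrylated gelatin.

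**The concern.** The analysis in 11.3 is descriptive and 11.1 states no hypothesis, so the reported frequency of adverse events is itself the primary result. Two definitions of that frequency stand in the protocol, and nothing says which governs. A related-only count can equal the all-event count or fall below it, never exceed it. In a single-arm, open-label study the filter would be the investigator's own causality judgement. That design is declared and is not an error, but it is a reason to fix the definition before data exist.

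Causality also feeds other outputs. Section 10.1 needs hydrogel-caused and surgery-caused events separately, and its overall safety grades depend partly on study-related side effects. If the recorded field refers to another product, or merges two causes in one answer, those outputs rest on reconstruction. A causality judgement not recorded at the time is hard to recover later.

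**Working it through.** This is mainly a comparison of text. The protocol states no adverse event rate, so there is no figure of its own to reproduce.

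**Step 1. Definition of the primary adverse event item.**

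| Place | Events covered | Status |
|---|---|---|
| 2.1 | all, including systemic symptoms | primary objective |
| 3.3.1, systemic sub-item | related only | primary |
| 10.1, first item | all, including systemic symptoms | primary |
| 10.1, next items | caused by the hydrogel; caused by surgery | secondary |

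Attributed events are therefore primary in 3.3.1 and secondary in 10.1.

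**Step 2. Status of the ophthalmic items.** All six topics in the ophthalmic list of 3.3.1 return in 10.1. They are primary in the first place and secondary in the second. Three of the six (delayed healing, infection, detachment) then stand under the primary-outcome heading in 10.1, so 10.1 gives those three both labels.

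**Step 3. Are any events lost?** Section 9.1 defines an adverse event whatever its relationship to treatment, 9.2 evaluates all events from enrolment to the end of the study, and 9.4 records each new one. So no: both an all-event and a related-event table could be drawn from the same records, provided causality is recorded properly.

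**Step 4. Is causality recorded properly?** Section 9.2.6 names the trial procedures and the hydrogel. Section 9.4 names the trial procedures and a transplanted cell product. The procedure half agrees and the product half does not. Section 13 likewise promises subjects a cell suspension, which suggests text carried over from another study rather than a fault of text extraction. A form built literally from 9.4 would have no entry for relationship to the hydrogel.

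**Step 5. Can one judgement fill two tables?** Both 9.2.6 and 9.4 describe one combined judgement. Section 10.1 needs two sets of events. A combined answer of, say, probably related does not show which set the event belongs to.

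**Step 6. How far could the definition move the rate?** This rests on assumptions. Let *p* be the proportion of the 30 subjects with any adverse event and *s* the share of those subjects with a related one. The related rate is *p* × *s* and the gap is *p* × (1 − *s*). Take *p* from 30% to 70% and *s* from 25% to 75%:

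- related rate: from 0.30 × 0.25 = 7.5% to 0.70 × 0.75 = 52.5%;
- gap: from 0.30 × 0.25 = 7.5 points to 0.70 × 0.75 = 52.5 points.

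This treats the relatedness filter as applied to every adverse event. Section 3.3.1 places it only in the systemic sub-item, so within these assumptions the figures show the most the wording could do, not an expected effect.

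**The case against.** The best defence is that the protocol works in practice. The word *related* sits only in the systemic sub-item of 3.3.1. The ophthalmic items beside it are unrestricted, and the expected events in 9.2.2 are mainly ocular. Sections 9.1 and 9.2 capture and evaluate every event. Section 9.2.6 requires a causality judgement that names the hydrogel, so the wording in 9.4 can be seen as a slip set against an operative rule. Infection, delayed healing and detachment have examination criteria in 10.1 and can be counted without a causality field. The study is exploratory and descriptive, so no test, threshold or power figure depends on the rate. The phrase in 2.2 can be read as the main measures for the secondary objective, since 3.3.2 lists thickness and clarity as secondary.

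Most of this stands, and it limits the consequence. A reader might infer that events cannot be attributed to the hydrogel at all, or that the relationship is never recorded. The documents do not support that, because 9.2.6 asks for the judgement and the fault lies in the recording item. A reader might also infer that the primary safety estimate is biased downward by some fixed factor. That does not follow either: all events are kept, and no rates are given from which to compute a factor.

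The defence does not reconcile 3.3.1 with 2.1 and 10.1, settle the status of the ophthalmic items, correct the product named in 9.4, or supply the separate judgements that 10.1 needs.

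**Conclusion.** The protocol is wrong as written on three matters: the definition of the primary adverse event item, the status of the ophthalmic safety items, and the causality item in 9.4. The first two make the primary safety result ambiguous. The third puts attribution to the hydrogel at risk, and the single combined judgement adds to that risk. The wording in 2.2 is untidy but does not create a competing primary endpoint.

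The conflicts can be read directly from the text and need no assumption. The risk to attribution assumes that the form is built from 9.4 as it stands. The numerical effect on the rate cannot be derived from the document. The range in the working depends on assumed rates and on a wider filter than 3.3.1 states. Sample size, type I error and power are not affected. The point should be settled before the first subject is enrolled, because it concerns how the primary objective is defined and recorded.

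**What to change.** 1. Delete *related* from the systemic sub-item of 3.3.1 and use one primary definition in 2.1, 3.3.1 and 10.1: occurrence, severity and frequency of all adverse events over the period in 9.2, from enrolment to the end of the study. Report related events as a named subset. A count that starts only at implantation would conflict with 9.2, and a bare any-event proportion would drop the severity and frequency that 2.1 asks for.
2. Replace the causality item in 9.4 with two items on the four-category scale of 9.2.6, one for the hydrogel and one for the trial procedures. Amend 9.2.6 so that it also asks for the two judgements separately.
3. Give the ophthalmic safety items the same status, primary or secondary, in 3.3.1 and throughout 10.1, including the heading above the judgement criteria. In 2.2, call thickness and clarity the *main efficacy measures*.

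The cost is protocol wording and one extra field on the case report form. The primary adverse event rate may look less favourable than a related-only rate would, but the related subset is still reported beside it.

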3.3.2 Secondary Evaluation Items: Efficacy Evaluation Items

- Corneal clarity / Corneal transparency
- Corneal thickness
- Visual acuity/Corrected visual acuity

3.4 Study Method Overview

This clinical study is a single-center, single-arm, open-label, single-dose trial evaluating the safety and efficacy (therapeutic effect) of a sutureless ophthalmic hydrogel for repairing corneal lamellar defects in patients with such defects.

The study consists of a screening period, an implantation period, and an observation period. After obtaining informed consent and completing registration, patients undergo screening examinations to confirm eligibility and absence of exclusion criteria. Surgery is performed under topical anesthesia. Following lesion debridement, the stromal bed is dried with a sponge, and a cotton pad is placed over the pupillary area to protect the fundus. The hydrogel, pre-liquefied in a 37°C water bath, is instilled into the lamellar defect using a sterile syringe, then irradiated with a 365 nm light source at an intensity of 18 mW/cm² for 30 seconds to achieve curing. A bandage contact lens may be applied after the procedure.

On postoperative day 1, gel integrity, thickness, and ocular surface inflammation are assessed using slit-lamp microscopy. During the 8-week observation period following gel injection, subjects are required to attend a total of four follow-up visits (Week 1, Week 2, Week 4, and Week 8). If any safety concerns arise from the trial results, necessary additional measures will be taken, and the specific ethics committee will be notified and must grant re-approval.

The safety of this clinical study will also be evaluated by the ethics committee. After completion of the first subject, the principal investigator may request an ethics

committee meeting based on the occurrence of serious adverse events or other relevant conditions, to seek advice on whether to continue the study or amend the clinical study protocol.

3.5 Expected Participant Involvement Duration

The expected participation period for each subject in this clinical study is from consent to the use of the sutureless ophthalmic hydrogel for corneal repair until the end of the observation period (8 weeks of postoperative follow-up).

4. Subject Inclusion/Exclusion/Discontinuation Criteria

4.1 Inclusion Criteria

Patients who meet all the following conditions are eligible for enrollment.

- 1) Patients with corneal stromal defects, including those caused by trauma or following lesion excision for infection, with a residual stromal thickness of ≥ 300 μm in the defect area.
- 2) Patients aged 18 to 85 years (inclusive, either sex) at the time of consent.
- 3) Patients who are capable of providing written informed consent voluntarily to participate in the study.

4.2 Exclusion Criteria

Patients meeting any of the following criteria will be excluded:

- 1) Patients with unexplained keratoconjunctival diseases.
- 2) Patients with severe dry eye, symblepharon, corneal neovascularization, or other ocular surface disorders.
- 3) Patients with systemic infectious diseases (positive for

bacteria/fungi/HBV/HCV/HIV/TP, etc.).

4) Patients with autoimmune diseases such as rheumatoid arthritis, Sjögren's syndrome, or graft-versus-host disease.

5) Patients with uncontrolled ocular diseases in the study eye.

6) Patients with major organ failure or other serious systemic conditions, including but not limited to: cardiac insufficiency; poorly controlled diabetes mellitus (fasting blood glucose >8 mmol/L despite glucose-lowering therapy); uncontrolled stage II or higher hypertension (blood pressure >160/100 mmHg despite antihypertensive therapy); history of malignancy within the past 5 years; severe immunodeficiency, etc.

6) Patients with psychiatric disorders that may interfere with treatment or evaluation.

8) Pregnant or lactating women, or women planning to become pregnant during the clinical study.

9) Patients deemed unsuitable for participation by the investigator.

10) Patients unable to complete follow-up visits.

4.3 Discontinuation Criteria

Subject participation will be discontinued under the following conditions, and after performing the scheduled examinations/observations/evaluations to the extent possible, the reason and course of discontinuation will be recorded in the case report form:

1) When the subject wishes to discontinue participation.

2) When, after obtaining consent, the subject is found not to meet the inclusion criteria or to violate the exclusion criteria.

3) When an adverse event occurs and it is determined that continuation of the study is difficult.

4) When the principal investigator and physician determine that the subject cannot comply with the protocol requirements.

5) When the clinical study itself is terminated.

Additionally, if a serious adverse event occurs, the principal investigator and physician shall report it to the ethics committee for regenerative medicine, etc.

5. Subject Informed Consent Acquisition/Registration

The principal investigator or physician provides oral and written explanation of the study's purpose, methods, etc., of the study to the subject and obtain written consent for study participation.

